Clinical Trial Protocol: NAV3-19

Study Title: A Prospective, Open-Label Trial of Comparing the Pathology Status of Lymphoseek®-Identified Sentinel Lymph Nodes Relative to the Pathological Pathology Status of Nonsentinel Lymph Nodes in Nodal Staging of Subjects With Known Cancer of the Cervix Who Are Undergoing Lymph Node Dissection

Study Number: NAV3-19

Study Phase: 2

Product Name: Lymphoseek®
[REDACTED] [REDACTED]

Investigators: Multicenter

Sponsor: Navidea Biopharmaceuticals
[REDACTED] [REDACTED]
[REDACTED]

	Date
Original Protocol:	27 May 2015
Amendment 1:	03 November 2015

Confidentiality Statement

This protocol and all of the information relating to it are confidential and proprietary property of Navidea Biopharmaceuticals

SYNOPSIS

Study title	A Prospective, Open-Label Trial of Comparing the Pathology Status of Lymphoseek®-Identified Sentinel Lymph Nodes Relative to the Pathological Pathology Status of Nonsentinel Lymph Nodes in Nodal Staging of Subjects With Known Cancer of the Cervix Who Are Undergoing Lymph Node Dissection
Study phase	Phase 2
Study objective(s)	
Primary Estimation of the per subject false negative rate (FNR) associated with the pathology status of Lymphoseek-identified sentinel lymph nodes (SLNs) relative to the pathology status of non-SLNs in the pelvic lymphadenectomy.
 
Secondary
 
• Estimation of sensitivity, negative predictive value (NPV), and overall accuracy of Lymphoseek-detected SLNs relative to the pathology status of non-SLNs.• Estimation of detection rate of SLNs by Lymphoseek and the rate of tumor detection in non-SLNs.• Determination of the proportion of lymph nodes identified intraoperatively by a dye (e.g., vital blue dye [VBD] or indocyanine green [ICG])that are also identified intraoperatively by Lymphoseek (i.e., concordance using the number of lymph nodes stained by the dye as the denominator).• Determination of reverse concordance comparing dye to Lymphoseek (i.e., using the number of lymph nodes identified intraoperatively by Lymphoseek as the denominator).• Comparison of pathologic assessment of the excised lymph node(s) to confirm the presence/absence of tumor metastases for Lymphoseek and dye on a per-subject basis.• Comparison of imaging and surgical findings 
Safety
 
• Evaluation of the incidence of adverse events
Study drug	Lymphoseek®
Dose(s)	50 µg Lymphoseek radiolabeled with 2.0 mCi (74 MBq) 99mTc

Route of administration	Intramucosal peritumoral injection in the subepithelial layer of the cervix
Duration of treatment	Single administration
Control	Pathology status of non-SLNs in the pelvic lymphadenectomy
US Indication	
Lymphoseek is a radioactive diagnostic agent indicated with or without scintigraphic imaging for:
 
 • Lymphatic mapping using a handheld gamma counter to locate lymph nodes draining a primary tumor site in patients with solid tumors for which this procedure is a component of intraoperative management. • Guiding sentinel lymph node biopsy using a handheld gamma counter in patients with clinically node negative squamous cell carcinoma of the oral cavity, breast cancer, or melanoma.
Main criteria for inclusion	
 1. Subject has provided written informed consent with HIPAA authorization 2. Has cervical cancer and is a candidate for surgical intervention, with lymph node dissection being a part of the surgical plan. 3. Is at least 18 years of age at the time of consent 4. Has an ECOG performance status of Grade 0 to 2 5. Has the following International Federation of Gynecology and Obstetrics (FIGO) IA2-IIA1 (≤ 4 cm) staging(Appendix 5). Subjects with a single enlarged/suspicious node on PET/CT will still be considered eligible as consistent with FIGO guidelines. 6. If of childbearing potential, the subject has a negative pregnancy test within 48 hours before administration of Lymphoseek, has been surgically sterilized, or has been postmenopausal for at least 1 year
Main criteria for exclusion	
 1. The subject has had preoperative chemotherapy, immunotherapy, or radiation therapy within the 30 days prior to Lymphoseek administration 2. Has had previous surgery or radiation to node basins that would be involved in the ILM procedure 3. Has a known allergy to dextran 4. Is breast-feeding or pregnant 5. Before the administration of Lymphoseek, has received any radiopharmaceutical within 7 radioactive half-lives of that radiopharmaceutical 6. Is scheduled for surgery and/or another invasive procedure other than the primary surgical intervention within the 3 days after Lymphoseek administration

	7. Has received an investigational product within the 30 days prior to Lymphoseek administration
Study design	Prospective, open-label, within-patient, multi-center study of Lymphoseek in the detection of lymph nodes in subjects with known cancer of the cervix. All subjects will receive a single dose of 50 µg Lymphoseek radiolabeled with 2 mCi (74 MBq) Tc 99m.
Methodology	
The proposed study includes: screening, enrollment, pre- and post-injection assessments, injection (Lymphoseek and dye), imaging and surgery.
 
Screening Visit (Day -29 to -1): The screening visit will include review of trial eligibility, informed consent, collection of medical history, vital signs, physical exams, clinical lab results, and review of medications.
 
Before Enrollment: Within 48 hours before Lymphoseek injection, a urine or serum pregnancy test will be performed for subjects of childbearing age.
 
Before Lymphoseek Injection: Vital signs will be collected.
 
Lymphoseek Injection: Subjects will receive a single dose of 50 µg Lymphoseek radiolabeled with 2 mCi (74 MBq) 99mTc at least 15 minutes but no more than 15 hours before the start of the surgical procedure. Lymphoseek will be administered peritumorally by intramucosal injection.
 
Post-injection: Vital signs will be collected. Lymphoscintigraphy will be completed prior to surgery and no later than 20 hours after Lymphoseek injection.
 
Surgery: Dye (e.g., VBD or ICG) may be administered in the operating room immediately before surgery. Fifteen minutes to 20 hours after Lymphoseek injection, subjects will undergo surgery to remove the primary tumor, and lymphatic mapping will be performed.
 
36 Hour Post-injection Follow-up: Vital sign assessment, physical examination, and review of adverse events and medications will be performed.

Planned trial dates	Start of study June 2015	End of Study July 2016
Planned number of trial centers / countries	Approximately 4 to 6 sites in the United States	
Number of subjects	Approximately 40 subjects will be enrolled. This sample size was chosen in order to provide exploratory results for the primary endpoint of FNR within this subject population. This study is not powered with respect to testing any statistical hypotheses.	
Primary endpoint	Per subject FNR	
Secondary endpoints	
• Per-subject sensitivity, NPV, and accuracy• Rate of tumor detection in SLNs and non-SLNs• Proportion of lymph nodes identified intraoperatively by dye (e.g., VBD or ICG) that are also identified intraoperatively by Lymphoseek (i.e., nodal concordance)• Proportion of lymph nodes identified intraoperatively by Lymphoseek that are also identified intraoperatively by dye (i.e., reverse nodal concordance)• Number of identified lymph nodes per subject by tracing agent (Lymphoseek or dye), per-subject concordance, and per-subject reverse concordance• Comparison of pathologic assessment of the excised lymph node(s) to confirm the presence/absence of tumor metastases for Lymphoseek and dye on a per-subject basis.• Number and anatomical locations of lymph nodes identified by preoperative Lymphoscintigraphy• Incidence of adverse events	
Plan for statistical analysis	
The following analysis populations will be defined for the study:
 
• Intent-to-Treat (ITT): enrolled subjects with administration of test medicine for whom at least one lymph node was removed with histopathology available• Per protocol (PP): ITT subjects without major protocol violations• Safety: enrolled subjects with administration of test medicine 
Primary endpoint primary analysis: The per subject FNR will
	

	
be computed using pathologically positive lymph nodes from all subjects in the ITT population. Along with reporting the number of false negative subjects and the observed FNR, an exact two-sided 95% confidence interval will be computed. A sensitivity analysis of the primary endpoint will be computed using the PP population.
 
All analyses of safety will be conducted on the safety population.

--	--

TABLE OF CONTENTS

SYNOPSIS.....	2
LIST OF IN-TEXT TABLES	11
LIST OF APPENDICES.....	11
LIST OF ABBREVIATIONS AND DEFINITIONS OF TERMS.....	12
TRIAL ADMINISTRATIVE STRUCTURE	14
INSTITUTIONS FOR TRIAL CONDUCT	14
1 INTRODUCTION	15
1.1 Background.....	15
1.1.1 Intraoperative Lymphatic Mapping (ILM)	15
1.1.2 Rationale for Evaluation of SLNB in Cervical Cancer.....	16
1.2 Previous Nonclinical Research and Clinical Trial Experience with Tilmanocept and Lymphoseek.....	18
2 STUDY OBJECTIVES.....	21
2.1 Primary Objective	21
2.2 Secondary Objectives.....	21
2.3 Safety Objective.....	21
3 OVERVIEW OF METHODOLOGY AND DESIGN.....	22
3.1 Overall Study Design.....	22

GCP	Good Clinical Practices
H&E	hematoxylin and eosin
HIPAA	Health Insurance Portability and Accountability Act of 1996
ICG	indocyanine green
ICF	informed consent form
ICH	International Conference on Harmonization
IEC	Independent Ethics Committee
IHC	immunohistochemical
ILM	intraoperative lymphatic mapping
IRB	Institutional Review Board
ITT	intent-to-treat
IV	intravenous
kDa	kilodaltons (molecular weight measure; 10^3 Da)
lbs	pounds
LN	lymph node
Lymphoseek	technetium Tc 99m tilmanocept
max	maximum
MBR	mannose binding receptor (CD206)
mCi	millicurie (10^{-3} Ci; 3.7×10^7 Becquerel or Bq)
MedDRA	Medical Dictionary for Regulatory Activities
μg	micrograms (10^{-6} g)
min	minimum
mL	milliliters (10^{-3} L)
mm	millimeters (10^{-3} m)
mmHg	millimeters of mercury
NCCN	National Comprehensive Cancer Network

nm	nanometers (10^{-9} m)
nmol	nanomoles (10^{-9} moles)
NPV	negative predictive value
PLND	pelvic lymphadenectomy
PP	per protocol
σ	sigma; standard deviation
SAE	serious adverse event
SAP	Statistical Analysis Plan
SLN	sentinel lymph node
SD	standard deviation
SNMMI	Society of Nuclear Medicine and Molecular Imaging
Sponsor	Navidea Biopharmaceuticals
Tc 99m	technetium-99m metastable isotope; γ -emitting ($t_{1/2} = 6.02$ h)
Tilmanocept	DTPA Mannosyl Dextran (the US Adopted Name for the drug substance of Lymphoseek)
TNM	tumor, lymph node, metastasis staging
US	United States
USFDA	US Food and Drug Administration
UTI	urinary tract infection
VBD	vital blue dye; Lymphazurin TM as 1% isosulfan blue for injection; USFDA-approved ILM colorimetric agent
WHO	World Health Organization

TRIAL ADMINISTRATIVE STRUCTURE

[figure not shown]
The principal investigator must sign the protocol signature page before trial participant recruitment may start. Likewise, all protocol amendments must be signed and dated by the principal investigator before coming into effect.

The name and address of the participating center, the investigators, and all required signature documents will be maintained in the trial master file (TMF).

In addition to the principal investigator, there are additional on-site roles that may be performed by other sub-investigators:

- Subject referral to the trial
- Review of subject eligibility and medical records
- Safety assessments
- Injection and imaging
- On-site image analysis

Trial personnel not listed in this section are identified in a separate personnel list. This list will be updated as needed. The list of personnel will be available in the center's investigator site file (ISF).

1 INTRODUCTION

[REDACTED]

10. **What is the primary purpose of the *Journal of Clinical Endocrinology and Metabolism*?**

1000

A solid black rectangular image with a thin white border on the right side. The image is oriented vertically and appears to be a scan of a document page.

[REDACTED]

[REDACTED] [REDACTED]

[REDACTED]

[REDACTED]

[REDACTED]

[REDACTED] [REDACTED]

[REDACTED] [REDACTED]

[REDACTED]

1. **What is the primary purpose of the study?** The study aims to evaluate the effectiveness of a new treatment for hypertension in a diverse population.

2 STUDY OBJECTIVES

2.1 Primary Objective

Estimation of the per subject FNR associated with the pathology status of Lymphoseek-identified SLNs relative to the pathology status of non-SLNs in the pelvic lymphadenectomy.

2.2 Secondary Objectives

Estimation of sensitivity, negative predictive value, and overall accuracy of Lymphoseek-detected SLNs relative to the pathology status of non-SLNs.

Estimation of the detection rate of SLNs by Lymphoseek and the rate of tumor detection in non-SLNs.

Determination of the proportion of lymph nodes identified intraoperatively by a dye (e.g., VBD or ICG) that are also identified intraoperatively by Lymphoseek (i.e., concordance using the number of lymph nodes stained by the dye as the denominator).

Determination of reverse concordance comparing dye to Lymphoseek (i.e., using the number of lymph nodes identified intraoperatively by Lymphoseek as the denominator).

Comparison of pathologic assessment of the excised lymph node(s) to confirm the presence/absence of tumor metastases for Lymphoseek and dye on a per-subject basis.

Comparison of imaging and surgical findings.

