7.2.7 Day 1: Imaging and Surgery

SPECT-CT will be performed prior to surgery as described in [Section 8.3](#) and in a manner consistent with the EANM clinical and technical guidelines for lymphoscintigraphy and sentinel node localization in gynaecological cancers as adopted by the SNMMI ([Giammarile et al., 2014](#)). All findings will be documented and recorded on the appropriate case report form (CRF). Dye (e.g., VBD or ICG) may be administered in the operating room immediately before surgical incision. The injection will be performed as deemed appropriate by the surgeon and in accordance with the standard of care at the clinical site. Imaging shall be completed prior to surgery and no greater than 20 hours after Lymphoseek injection, subjects will undergo ILM, SLN(s) will be harvested and surgery to remove the

primary tumor will be completed. Location of both hot and dye-identified nodes will be recorded on the sponsor-provided intraoperative worksheets.

7.2.8 24 ± 12 hours Postsurgical Safety Follow-up (telephone)

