8.3 Lymphoscintigraphy (SPECT/SPECT-CT Image Acquisition)

The SPECT camera used to obtain the images should be equipped with a low-energy, high-resolution collimator with a 20% window centered over a 140keV peak. The subject should be imaged in the same position used for surgery with arms positioned out of the field of view. Dynamic imaging should start at the time of injection and planar imaging should commence between 15 minutes and 20 hours post injection. Subjects should void their bladder just prior to imaging. It is strongly recommended that each site should perform all imaging acquisitions per their camera manufacturer and model parameters and in accordance with their institutional practices. All imaging should be completed prior to surgery no greater than 20 hours after injection.

For Sites using a SPECT camera:

Dynamic Imaging (optional)	Planar Imaging (mandatory)
Start at time of injection and continuously acquire until nodal uptake is seen, but for no longer than 1 hour.	To start after dynamic imaging (if performed) or to begin no sooner than 15 minutes post injection. Total acquisition time should not exceed 1 hour.

For sites using a SPECT/CT hybrid camera:

Dynamic Imaging (optional)	Planar Imaging (mandatory)
CT portion should be done prior to injection and start of SPECT. SPECT portion should start at time of injection and continuously acquire until nodal uptake is seen, but for no longer than 1 hour.	To start after dynamic imaging (if performed) or to begin no sooner than 15 minutes post injection. Total acquisition time should not exceed 1 hour. A CT scan for attenuation correction should be performed prior to each planar image.

Low-dose CT parameters for each institution's camera make/model should be utilized. SPECT data should be iteratively reconstructed and attenuation correction should be applied.

All images (non-corrected, corrected SPECT , CT and fused SPECT/CT) should be reviewed by a radiologist for quality.

[REDACTED] The number and anatomical location of each probable lymph node(s) identified preoperatively will be documented and captured in the eCRFs.

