9.4.2 Secondary Efficacy Variables

The secondary efficacy variables are the following:

- Per-subject sensitivity, defined as the number of subjects with at least one pathologically positive SLN divided by the number of subjects with at least one pathologically positive node (SLN or non-SLN)
- Per-subject negative predictive value (NPV), defined as the number of subjects with no pathologically positive lymph nodes (SLNs or non-SLNs) divided by the number of subjects with pathologically negative Lymphoseek-identified SLN(s) (or no SLNs were detected)
- Per-subject accuracy, defined as the proportion of subjects whose lymph nodes were either all pathologically negative (i.e, true negative subject) or at least one SLN was

pathologically positive (i.e., true positive subject) divided by the number of subjects in the analysis population

- Rate of tumor detection in SLNs, defined as the proportion of subjects with at least one pathologically positive SLN divided by the number of subjects in the analysis population
- Rate of tumor detection in non-SLNs, defined as the proportion of subjects with at least one pathologically positive non-SLN divided by the number of subjects in the analysis population
- Nodal concordance, defined as the proportion of lymph nodes identified intraoperatively by dye (e.g., VBD or ICG) that are also identified intraoperatively by Lymphoseek
- Subject concordance, defined as the number of subjects whose lymph nodes that were identified intraoperatively by dye were also all identified intraoperatively by Lymphoseek
- Reverse nodal concordance, defined as the proportion of lymph nodes identified intraoperatively by Lymphoseek that are also identified intraoperatively by dye
- Subject reverse concordance, defined as the number of subjects whose lymph nodes that were identified intraoperatively by Lymphoseek were also all identified intraoperatively by dye
- Number of SLNs per subject
- Number of lymph nodes identified intraoperatively by dye
- Number and anatomical locations of lymph nodes identified by preoperative Lymphoscintigraphy

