Along with reporting the total number of subjects with at least one pathologically positive non-SLN and the observed rate of non-SLN tumor detection, an exact two-sided 95% confidence interval will be computed

The nodal concordance, P_1 , will be computed as follows using lymph nodes from all subjects in the ITT population:

$$P_1 = \frac{\text{Number of SLNs identified intraoperatively by VBD or ICG}}{\text{Number of lymph nodes identified intraoperatively by VBD or ICG}}$$

9.9.4.1 Along with reporting the number of SLNs identified intraoperatively by VBD or ICG and the observed nodal concordance, an exact two-sided 95% confidence interval will be computed.

The subject concordance, P_2 , will be computed as follows using all subjects in the ITT population:

$$P_2 = \frac{\text{Subjects whose lymph nodes that were intraoperatively identified by VBD or ICG were also all identified by Lymphoseek}}{\text{Subjects with at least one lymph node intraoperatively identified by VBD or ICG}}$$

Along with reporting the number of subjects in the numerator and the observed subject concordance, an exact two-sided 95% confidence interval will be computed.

The reverse nodal concordance, P_3 , will be computed as follows using lymph nodes from all subjects in the ITT population:

$$P_3 = \frac{\text{Number of SLNs identified intraoperatively by VBD or ICG}}{\text{Number of SLNs}}$$

Along with reporting the number of SLNs identified intraoperatively by VBD or ICG and the observed reverse nodal concordance, an exact two-sided 95% confidence interval will be computed.

The subject reverse concordance, P_4 , will be computed as follows using all subjects in the ITT population:

$$P_4 = \frac{\text{Subjects whose SLNs were also all identified by VBD or ICG}}{\text{Subjects with at least one SLN}}$$

Along with reporting the number of subjects in the numerator and the observed reverse subject concordance, an exact two-sided 95% confidence interval will be computed.

The average number of SLNs per subject will be computed, along with a 95% confidence interval.

The average number of lymph nodes identified intraoperatively by dye per subject will be computed, along with a 95% confidence interval.

The average number of lymph nodes identified by preoperative Lymphoscintigraphy per subject will be computed, along with a 95% confidence interval.

The number and percent of lymph nodes identified by preoperative Lymphoscintigraphy will be reported per anatomical location.

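### The secondary objective of comparing imaging with surgery has no paired endpoint or analysis

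*Combined protocol and SAP*

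**What the plan says.** The objective "Comparison of imaging and surgical findings" appears in the synopsis and closes the list in section 2.2. Neither place gives a unit of analysis, a matching rule or a measure of agreement. Section 3.1 describes the study as within-subject and ties the 40 subjects to exploratory results for both the primary and the secondary objectives.

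The only imaging variable in section 9.4.2 is "Number and anatomical locations of lymph nodes identified by preoperative Lymphoscintigraphy". Section 9.9.4 turns it into two outputs. One is a mean count of imaged nodes for each subject, reported with a 95% interval. The other is a location table, described as follows: "The number and percent of lymph nodes identified by preoperative Lymphoscintigraphy will be reported per anatomical location".

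On the surgical side, the nearest counterpart is "The average number of SLNs per subject will be computed, along with a 95% confidence interval". A mean count of dye-identified nodes is planned in the same way.

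The data for a comparison are to be collected. For imaging, section 8.3 states: "The number and anatomical location of each probable lymph node(s) identified preoperatively will be documented and captured in the eCRFs". For surgery, section 7.2.7 states: "Location of both hot and dye-identified nodes will be recorded on the sponsor-provided intraoperative worksheets".

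**The concern.** A comparison of what the scan showed with what the surgeon found is a paired question: it asks about the same subject and the same location. Two means and a one-sided location table are marginal summaries. They can show that the scan and the probe found similar numbers of nodes on average, but not that these were the same nodes. If the plan is followed as written, the report will not say how often an imaged location yielded an SLN, or how often an SLN lay where the scan showed nothing.

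The contrast with the dye objective is marked. For dye against Lymphoseek, the protocol defines forward and reverse concordance at node and subject level, with numerators, denominators and exact intervals. The imaging objective has no counterpart. If agreement is worked out later, the matching level, the denominator and the handling of subjects with nothing to match will be chosen after the data of an open-label study have been seen.

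**Working it through.** **1. Trace the objective through section 9.9.4.**

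| Planned output | Uses imaging | Uses surgery | Linked within subject |
|---|---|---|---|
| Mean imaged nodes per subject, 95% CI | yes | no | no |
| Imaged nodes by location, n and % | yes | no | no |
| Mean SLNs per subject, 95% CI | no | yes | no |
| Mean dye-identified nodes per subject, 95% CI | no | yes | no |
| Concordance measures P1 to P4 | no | yes | dye against Lymphoseek only |

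P1 has the denominator "Number of lymph nodes identified intraoperatively by VBD or ICG". P2 to P4 are likewise built only from dye-identified nodes and SLNs. No row combines imaging with surgery, and none tabulates surgical nodes by location.

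**2. Check for deferral.** Section 9.9.5 leaves additional safety analyses to the Statistical Analysis Plan. No efficacy analysis is deferred there.

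**3. What the planned outputs can reveal (assumed data, logical bound only).** Take 40 subjects, each with one imaged node and one SLN, and 20 left and 20 right in each data set. Let k be the number who are left on both. The remaining cells follow:

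- left on imaging, right at surgery: 20 − k
- right on imaging, left at surgery: 20 − k
- right on both: k

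Agreement = 2k/40, with k from 0 to 20, so it runs from 0/40 to 40/40. For every k the planned outputs are the same: mean imaged nodes 1.0, mean SLNs 1.0, imaged locations 50% and 50%.

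The same holds with more nodes. Assume 80 imaged nodes and 80 hot nodes, 2.0 per subject on each side. If m nodes are common to both, there are 160 − m distinct nodes, and the share of imaged nodes found at surgery is m/80. This runs from 0% (160 distinct nodes) to 100% (80 distinct nodes) with both means unchanged.

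**4. Precision of a per-subject agreement proportion.** The plan gives no figure for this objective. Its one precision figure, in section 9.7, concerns the false negative rate: 0.20 × 40 = 8 subjects, and 1/8 has an exact 95% interval of 0.3% to 52.7%, half-width 26.2%. That reproduces the stated 26%, and this point does not touch it.

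The same exact method uses these limits for x agreeing subjects out of n:

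- lower = Beta quantile at 0.025 with parameters x and n − x + 1
- upper = Beta quantile at 0.975 with parameters x + 1 and n − x

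With assumed counts and n = 40:

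| Agreeing subjects | Exact 95% CI | Half-width (points) |
|---|---|---|
| 36/40 | 76.3% to 97.2% | 10.4 |
| 32/40 | 64.4% to 90.9% | 13.3 |
| 28/40 | 53.5% to 83.4% | 15.0 |
| 20/40 | 33.8% to 66.2% | 16.2 |

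**5. Why the rule for unmatched subjects must be stated.** Suppose 36 of 40 subjects had an imaged node and 32 agreed fully. Leaving out the other 40 − 36 = 4 gives 32/36 = 88.9%. Counting them as disagreeing gives 32/40 = 80.0%.

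**The case against.** The objective is one short phrase and does not mention matching by node, side or station. A sponsor could say that mean imaged nodes beside mean SLNs, each with an interval, is a comparison of a kind, and that the location table goes beyond counting. Both observations are correct, so it would be unfair to say that the plan only counts nodes on the scan. But comparing two means compares average yield, not findings, and the location table has no surgical counterpart. In a study described as within-subject, the paired reading is the natural one. Even on the loosest reading, the objective has no defined measure.

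A reader might infer that the trial will be unable to answer the question. The documents do not support that: locations are recorded on both sides, so agreement could probably still be derived. The gap lies in pre-specification.

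A reader might also take the range of 0% to 100% as a realistic spread. It is not. Scan and probe detect the same tracer injection in the same subject, so near-zero agreement is implausible. The range shows only that the planned outputs carry no information on agreement.

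Finally, the study is exploratory and unpowered, and this is one secondary objective among several. That limits the weight of the point, but an exploratory estimate still needs a numerator and a denominator.

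**Conclusion.** The point holds: a stated secondary objective has no paired endpoint or analysis in the protocol text, and the summaries that are planned cannot stand in for one. It is a moderate, easily corrected gap. The primary false negative rate, the sample size and the safety analyses do not depend on it.

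The conclusion assumes that the comparison is meant within subject, and it is limited to the visible text. Section 8.3 has a redaction just before the sentence on recording imaged nodes, but sections 9.4.2 and 9.9.4 show none. The worksheet and eCRF are not shown, so whether they already share location terms is unknown.

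Two extensions that a reader might want are not supported:

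- **Tumour-positive non-SLNs in locations not seen on imaging.** Section 7.2.7 requires locations only for hot and dye-identified nodes, and section 8.5.1 requires individual identification in the pathology report only for SLNs. The result may not be computable for other nodes. With about 8 node-positive subjects expected, it would also rest on very few.
- **Results split by type of image acquisition.** With 40 subjects the groups would be too thin to be useful.

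**What to change.** Add the following to sections 9.4.2 and 9.9.4, in ITT subjects with imaging, by side and anatomical station, modelled on the dye concordance measures:

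- (a) the proportion of imaged locations with at least one SLN, using the analysis definition in section 8.4.3 (hot ex vivo);
- (b) the proportion of SLN locations that were seen on imaging;
- (c) the proportion of subjects with complete location agreement, with an exact two-sided 95% confidence interval.

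State in advance how subjects with no imaged node, no SLN, or neither enter each measure. Measures (a) and (b) pool several locations from one subject, so the exact interval belongs on (c).

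Use one list of sides and stations on the imaging eCRF and the intraoperative worksheet. Because SLN status is decided ex vivo, make sure that the worksheet carries a location for every node that qualifies.

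Optionally, list the subjects whose tumour-positive SLN lay in a location not seen on imaging, as description only.

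The cost is wording in two sections, a shared location list and a small amount of programming. No new procedure and no additional subject is needed.
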